9.5.3.2 Exploratory Analyses

Post hoc tests may be performed to test for differences in the efficacy endpoints between the CGS-200-0 (Vehicle), CGS-200-1 and CGS-200-5 treatment groups for exploratory purposes.

9.5.4 Tolerability Analyses

The primary tolerability endpoint will be tolerability of the formulations on each of Days 1, 2, 3, and 4. On each of these days, subjects will report an NRS score for burning / stinging at the application site pre-treatment and during treatment, and a

pre-treatment and during treatment pruritus score. Pre-treatment and during treatment erythema and scaling scores will be recorded by clinic staff assigned to the study. This will be done at 0, 15, 30, 60, and 90 minutes after application to capture time points during treatment and after washing the application site. The score for each of the above tolerability variables will be entered as a value at each assessment time. For each subject an "area under the curve" (AUC) calculation will be performed in 90 minute intervals for each score value. The AUC's for tolerability variables combined will be compared between the CGS-200-5-and CGS-200-0 treatment groups.

9.5.5 Safety Analyses

9.5.5.1 Adverse Events

The incidence of all reported AEs and treatment-emergent AEs (TEAE) will be tabulated. A TEAE is defined as an event that first occurs or worsens in intensity after the administration of study drug. AEs will be classified by system organ class and preferred term using the Medical Dictionary for Regulatory Activities (MedDRA). The severity of the AE will be graded using the RCTC v2.0 whenever possible. For AEs that are not included in the RCTC v2.0, the grading categories (mild, moderate, severe, and life-threatening) will be used and equated to the respective RCTC grade (Grades 1, 2, 3, and 4). For incidence reporting, if a subject reports more than one AE that is coded to the same system organ class or preferred term, the subject will be counted only once for that specific system organ class or preferred term.

An overview of AEs, which includes subject incidence of TEAEs, treatment-related AEs, severity of AEs, SAEs, deaths, and AEs leading to discontinuation, will be presented. For AEs presented by severity, the worst severity during the study will be presented for each subject. The subject incidence of TEAEs will be summarized by system organ class and preferred term. The subject incidence of treatment-related AEs and RCTC v2.0 toxicity grade will be summarized by preferred term.

9.5.6 Vital Signs

Descriptive summaries of the vital signs (both raw and change from baseline values) including blood pressure, heart rate, respiratory rate, and body temperature will be prepared for each dose group. Descriptive statistics for quantitative variables will include sample size, mean, standard deviation, standard error, median, minimum, and

maximum. The 95% confidence interval of the mean will be constructed if it is appropriate (when there is more than 1 subject in a cohort).

Vital sign values will be classified as low, normal or high based on the cut-off points defined below, and the data will be summarized by presenting shift tables from baseline to each post-baseline visit. For Baseline vital sign measurements:

Measurement	Lower	Upper	Unit
Temperature	<35.0	>38.0	С
Systolic Blood Pressure (BP)	<110	>135	mmHg
Diastolic BP	<65	>85	mmHg
Heart Rate	<50	>110	beats/min
Respiratory Rate	<12	>20	breaths/min

For Post-baseline vital sign measurements:

Measurement (unit)	Low	High
Systolic Blood Pressure (mm Hg)	≥ 20 point decrease from baseline	≥ 20 point increase from baseline
Diastolic Blood Pressure (mm Hg)	≥20 points decrease from baseline	≥ 20 point increase from baseline
Pulse (beats per minute (bpm))	< 50 and decrease from baseline ≥ 15	> 100 and increase from baseline ≥ 15
Temperature (C)	<35	>38
Respiratory Rate (breaths per min)	<12	>20

9.5.7 Interim Analyses

Interim analyses will be performed at Days 19, 35, and 64 per 9.5.3 and 9.5.3.1 above,

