3.0 STUDY DESIGN

3.1 OVERALL STUDY DESIGN

This is a multi-center, randomized, double-blind clinical trial to examine the comparative effects on OAKP of CGS-200-1 (1% Capsaicin content) (N=40), CGS-200-5 (5% Capsaicin content) (N=40), and CGS-200 Vehicle (no Capsaicin) (N=40) in subjects with OA of the knees according to the 1986 ACR criteria. Assigned doses will be applied at the clinic for 60 minutes on each of four consecutive days.

Subjects will be randomized to one of the three Arms in this study: CGS-200-1 or CGS-200-5 or CGS-200-0 (Vehicle). All subjects will receive 4 consecutive days of treatment and will then be followed up until the Day 94 visit.

Subjects will receive the study arm appropriate treatment as a topical application over the frontal aspect of the knee(s) once daily on four consecutive days. The applications will be at the clinic but by the subject wearing gloves under supervision of clinic personnel. The application will be left in place for 60 minutes and then washed off at the clinic by clinic personnel. The amount of Investigational Drug Product to be applied is estimated to be approximately 0.13 mL based on experience in prior studies. Even though both knee(s) will receive application of study test materials, with regard to reduction in WOMAC pain and VAS pain score associated with study treatments, only one knee will be indicated as the "Study Knee". This will be the knee with the highest WOMAC pain score at baseline. If both knees have equal WOMAC pain scores at baseline, then the right knee will be considered the "Study Knee" with regard to WOMAC pain and VAS pain score reduction.

Data will be collected from Day 1 through Day 5 and then again on Days 19, 35, 64, and 94 for efficacy, tolerability, and safety measures. The Investigators, all site staff and Clinical Research Organization (CRO) personnel (except the Medical Monitor providing safety oversight) directly involved in the study will remain blinded to the treatment assignment throughout the trial.

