4.2 REPLACEMENT OF SUBJECTS

Subjects that do not receive 4 complete consecutive daily doses and/or drop out before completing the Day 35 visit may be replaced if the reason for dropping out is other than lack of drug product tolerability. A dose will be considered complete when at least 80% has been delivered on any study drug administration day; dosing will be considered complete overall when a total of at least 80%, in the aggregate, has been delivered across all study treatment days. Subjects that drop out or who cannot be followed up from after the Day 5 visit until the Day 35 visit may be replaced. Up to 10 subjects per arm may be replaced.

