9.5.3 Efficacy Analyses

Primary Efficacy Endpoint

The group mean LMS difference between each Active Treatment Arm and the Vehicle Arm for the WOMAC pain score at Day 35 will be tested for significance of difference at a significance value of $p \le 0.05$.

Secondary Efficacy Endpoints

The group mean LMS difference between each Active Treatment Arm and the Vehicle Arm for the WOMAC stiffness, function and total score at Day 35 will be tested for significance of difference at a significance value of p < 0.05

Also, the group mean reduction in OA knee pain score on a 100 mm VAS scale for each active treatment arm will be compared to the vehicle arm and tested for significance of difference at a significance value of p < 0.05

For dose-response estimation:

The group mean LMS difference between the 5% and the 1% Active Treatment Arms for the WOMAC pain, stiffness, function and total score at Day 35 will be tested for significance of difference at a significance value of $p \le 0.05$

Efficacy analyses will be carried out on the mITT set.

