9.5.3.1 Clinical Response

Clinical response will be measured by reduction of WOMAC pain score. In order for a subject to be considered to have successfully obtained a clinical response, the following criteria must be met:

WOMAC pain score reduced to 50% or less of baseline at any of the stated assessment times.

The durability of clinical response up to Day 94 will be evaluated by a tabulation of clinical response at a Days 19, 35, 64, and the Day 94 visit by treatment group. Subjects who have successfully met the above criteria (reduction of a least 50% in NRS pain score) at the Day 5 visit and who remain at least at this reduction of pain score or lower at the Day 35 visit will be considered to have a durable clinical response. Subjects who at the Day 35 visit have less reduction in WOMAC in OAKP score than they did at the Day 5 assessment will be considered to have failed to achieve a durable clinical response.

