10.6 DATA MANAGEMENT RESPONSIBILITIES

For data coding, the following medical dictionaries will be used:

- AEs and concomitant diseases: MedDRA;
- Concomitant medication: World Health Organization (WHO) Drug

Visual and computerized methods of data validation will be applied in order to ensure accurate, consistent and reliable data for the subsequent statistical analysis. These

procedures aim to detect out-of-range values, contradictory data, abnormal evolutions over time, and possible undetected protocol violations (eligibility criteria, time and medication compliance, etc.).

Data Management and the study monitor will generate electronic queries for resolution by the site.

The database will be locked in order to protect write access after the following preconditions are fulfilled:

- All data are entered in the database
- All data queries are resolved
- All necessary quality checks, in accordance with appropriate Standard Operating Procedures (SOPs), have been performed
- Decisions have been made and agreed as to the identities of all protocol violators
- All eCRFs have been source verified by the study monitor in the remote data capture (RDC)
- All eCRFs have been approved by the Investigator in the RDC system
- Written authorization from Vizuri Health Sciences is obtained.

Upon completion of the study and resolution of all outstanding queries, Data Management will lock the database and generate the SAS datasets necessary for data analysis and reporting.

The Data Management group will use the Clinical Database for storing and managing all data generated by this trial.

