4.2 Analysis Sets

The following three analysis sets will be defined for this study:

The intent-to-treat (ITT) set will be defined as all randomized subjects, whether or not they receive study drug.

The modified ITT (mITT) set will be defined as the subset of the ITT subjects that receive at least one dose of study medication and have at least one evaluable post-dosing efficacy endpoint. The mITT set will be defined based on randomized treatment rather than treatment actually received.

All efficacy analyses will be carried out using the mITT set.

The safety (SAF) set will be based on the ITT subjects who have received at least one dose of study medication (based on the treatment actually received rather than randomized treatment). All safety analyses will be carried out using the SAF set.

The Per Protocol (PP) set will include all mITT subjects in whom there were no major protocol deviations. Major protocol deviations for defining the PP analysis set will be identified by Vizuri prior to the database lock. If deemed appropriate, the analyses on primary and secondary efficacy endpoints listed in Section 6.1 and 6.2 will be repeated using the PP set.

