8. INTERIM ANALYSES

The scope of this document details the final analysis to be performed by CTI, and does not describe any interim analysis that may be performed.

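### Protocol 9.5.7 plans by-arm interim efficacy analyses without saying who runs or sees them, while the sponsor's exclusion decisions stay open until a later database lock

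*Protocol*

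**What the plan says.** Protocol 9.5.7 is a single sentence: "Interim analyses will be performed at Days 19, 35, and 64 per 9.5.3 and 9.5.3.1 above". The two sections it points to are by-arm analyses. Section 9.5.3 tests "The group mean LMS difference between each Active Treatment Arm and the Vehicle Arm for the WOMAC pain score at Day 35", and section 9.5.3.1 calls for a "tabulation of clinical response at a Days 19, 35, 64, and the Day 94 visit by treatment group". SAP section 8 limits itself to the final analysis and "does not describe any interim analysis that may be performed".

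On blinding, Protocol 3.1 says that investigators, site staff and CRO personnel (Medical Monitor excepted) "directly involved in the study will remain blinded to the treatment assignment throughout the trial". The synopsis, Protocol 9.2 and SAP 3.2.2 add the subjects. None of these lists includes the sponsor.

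On decisions about the data, Protocol 9.5.9 lets the sponsor remove subjects or individual values from the efficacy evaluation when it judges that a protocol violation harms interpretation. SAP 4.2 says "Major protocol deviations for defining the PP analysis set will be identified by Vizuri prior to the database lock". Among the preconditions for lock, Protocol 10.6 lists "Decisions have been made and agreed as to the identities of all protocol violators", and it places the lock after the study is complete. Under Protocol 4.2, subjects who miss doses or "drop out before completing the Day 35 visit may be replaced", provided the reason is not poor tolerability.

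**The concern.** Settling exclusions before database lock protects a trial only if the people settling them have not seen results by arm. Here the protocol commits to by-arm efficacy results at intermediate visits, and the only lock comes after the last of them. The party that holds the discretion over exclusions is also the one party that the blinding text does not cover.

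At stake is the credibility of the efficacy comparison. A sponsor that knows which way the arms are leaning could, without any bad intent, judge borderline violations differently. A reader of the study report could not tell whether that had happened.

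**Working it through.** **1. What a look contains.** Neither the 9.5.3 tests nor the 9.5.3.1 table can be produced without treatment codes. The WOMAC tests in the body of 9.5.3 are set at Day 35, and its VAS comparison names no day. The synopsis lists Days 5 to 94 for stiffness, function and total score. So at Days 19 and 64 the only content that is clear from the body text is the responder table by arm.

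**2. Who could run it.** CRO staff other than the Medical Monitor stay blinded, and SAP sections 4 and 8 give the CRO the final analysis only. No independent committee or separate unblinded statistician appears. The documents therefore name nobody who is permitted to run a by-arm interim, and nobody as its recipient.

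**3. What is still open, and until when.**

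| Item | Who decides | Timing stated |
|---|---|---|
| By-arm looks (Protocol 9.5.7) | not stated | Days 19, 35, 64; data cut not stated |
| Removing subjects or single values from efficacy (Protocol 9.5.9) | sponsor | no deadline |
| Identifying protocol violators (Protocol 10.6) | not stated | before lock |
| Major deviations for the per-protocol set (SAP 4.2) | sponsor | before lock |
| Replacing dropouts (Protocol 4.2, SAP 3.2.1) | not stated | no decision deadline; applies to events before the Day 35 visit |
| Database lock (Protocol 10.6) | data management, with sponsor authorisation | after study completion; follow-up runs to Day 94 |

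Every deadline for exclusions is the lock or later, and the lock follows all three named looks.

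**4. The plan's own figure.** SAP section 9 gives 80% power for a 63-point difference, SD 100, 40 per arm, two-sided 5%.
- Standard error: 100 × √(2/40) = 22.36.
- Power: Φ(63/22.36 − 1.960) = Φ(0.857) = 80.4%. The noncentral-t version gives 79.5%.

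The figure reproduces. It assumes one analysis of a dataset fixed without knowledge of results.

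**5. Size if exclusions were chosen with knowledge of results.** This is an illustration on assumptions that are not in the documents: no true difference, normal outcomes, 40 per arm, a two-sample t-test at two-sided 0.05 (simpler than the SAP's ANCOVA), and 40,000 simulated trials per row. Only significant results favouring active are counted. The k least favourable active subjects are then removed.

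| k removed of 40 | Error favouring active, none removed | After removal |
|---|---|---|
| 1 | 2.5% | 4.7% |
| 2 | 2.6% | 7.4% |
| 3 | 2.5% | 10.6% |

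This is a worst case. It needs subject-level results by arm, and it needs the least favourable subjects to have a violation that could justify removal.

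**The case against.** The best defence is that nothing here is shown to bias the primary test. Day 35 is the primary time point, no stopping rule or sample-size change hangs on the looks, and SAP 4.5 calls the study exploratory. If the looks change nothing and exclusions are fixed blind, the Day 35 test keeps its nominal 5%. That stands. Efficacy is analysed on the mITT set, and the per-protocol repeat is optional. Protocol 9.5.9 requires a protocol violation and a reported reason. The SAP does not repeat that exclusion clause, and its section 4.4 includes all dosed subjects' data when appropriate. These points limit the harm, but the SAP does not withdraw 9.5.9, and a reason reported afterwards does not show when the choice was made.

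A second defence is that 9.5.7 may mean only intermediate-visit summaries. Its days match those in the 9.5.3.1 table, Protocol 10.6 and SAP 4.1 describe one lock before analysis, SAP 8 treats interims as optional, and the sentence in 9.5.7 ends on a comma. That reading is possible, but the text calls them interim analyses that will be performed. If summaries are meant, the protocol should say so.

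A reader might infer more than the documents support:

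- **That the blind is broken.** The promise in 3.1 covers investigators, sites and CRO, so a look on the sponsor's side does not contradict it. The plan simply does not say how the two fit together.
- **That Day 64 and Day 94 scores will be contaminated.** Those scores are self-reported by blinded subjects, and nothing says that interim results reach sites. Leakage is a possibility that no text rules out, not a consequence of the plan.
- **That all later data follow the Day 35 look.** That depends on a data cut that 9.5.7 does not give. With staggered enrolment, many subjects could already have later visits.
- **That replacement lets the sponsor remove poor responders.** Ten per arm is a cap, limited to incomplete dosing or dropout for reasons other than tolerability. A replaced subject who was dosed and has an evaluable post-dose efficacy endpoint stays in the mITT set.

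**Conclusion.** The point holds in a limited form. Protocol 9.5.7 commits to by-arm interim efficacy analyses with no purpose, data cut, performer or recipient, and the SAP does not supply them. The sponsor is not listed as blinded, and its decisions on efficacy exclusions and per-protocol deviations need not be fixed until a lock that comes after those looks. Exclusions can therefore be decided after results by arm are known.

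This is a missing safeguard, not a demonstrated loss of error control. Its size runs from nothing, if exclusions are fixed blind, to the illustrated worst case of about 4.7% to 10.6% against 2.5% in one direction. The conclusion assumes that 9.5.7 means what it says and that no separate document, such as a blinding or unblinding plan, closes the gap.

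**What to change.** **Move the deadline.** In Protocol 9.5.7 and 9.5.9 and SAP 4.2 and 8, require that the following be fixed and signed before any between-arm analysis, instead of before database lock, for the subjects and data in that look:
- subject and single-value exclusions under 9.5.9;
- the list of protocol violators;
- per-protocol membership;
- replacement decisions.

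**Then choose one route and state it identically in both documents.**
- Run all by-arm efficacy analyses once, after the final lock.
- Or, for any look that is kept (for example one Day 35 readout after the last subject's Day 35 visit), state its purpose, content and data cut. Name an unblinded analyst separate from the blinded CRO team. Release group-level results only, to named recipients who are not at sites, not monitors and not deciding later exclusions.

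Dropping the Day 19 and Day 64 looks is the simplest course but not the only one, since specifying them properly also closes the gap.

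**Cost.** Wording in the protocol and SAP, plus a separate analyst if a look is kept. No patients, visits or data are added. The sponsor delays or gives up early looks that no stated rule uses.

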9.5.8 Procedures for Missing, Unused and Spurious Data

Missing values will not be substituted by estimated values but treated as missing in the statistical evaluation. All data from all subjects dosed in the study will be included in all listings, plots, summary tables, and statistical analyses when appropriate.

9.5.9 Rules for Excluding Subjects from Analysis

All dosed subjects will be included in the analyses of safety. The sponsor will make any decisions regarding whether any subjects or any individual values belonging to a subject will be excluded from the efficacy evaluations when the protocol violation is considered to have a negative impact on the scientific aspects and interpretation of the study results. If the subject has received any study drug, all available safety data will be used. The reason(s) for any exclusion will be described in the report.

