9.3 ANALYSIS SETS

The following three analysis sets will be defined for this study:

The intent-to-treat (ITT) set will be defined as all randomized subjects, whether or not they receive study drug.

The modified ITT (mITT) set will be defined as the subset of the ITT subjects that receive at least one dose of study medication and have at least one evaluable post-dosing efficacy endpoint. The mITT set will be defined based on randomized treatment rather than treatment actually received. All efficacy analyses will be carried out using the mITT set.

The safety (SAF) set will be based on the ITT subjects, but will be based on the treatment actually received rather than randomized treatment. All safety analyses will be carried out using the SAF set.

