9.5.10 Procedures for Reporting Deviations from Original Statistical Plan

Any deviations from the statistical analysis outlined in this protocol will be described, and reasons for the deviations listed, in the final Clinical Study Report.

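### Protocol 9.5.9 lets the sponsor drop subjects or values from efficacy with no blinding condition, which is unreconciled with the all-mITT rule and not withdrawn by the SAP

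*Protocol*

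**What the plan says.** **The exclusion rule.** Protocol 9.5.9 gives the decision to the sponsor: "The sponsor will make any decisions regarding whether any subjects or any individual values belonging to a subject will be excluded from the efficacy evaluations". The condition is "when the protocol violation is considered to have a negative impact on the scientific aspects and interpretation of the study results". The section names no categories of violation and sets no blinding condition. It does require the report to give reasons for any exclusion. Protocol 9.5.10 adds a general reporting duty: "Any deviations from the statistical analysis outlined in this protocol will be described".

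**The population rule.** Protocol 9.3 says "All efficacy analyses will be carried out using the mITT set", and Protocol 9.5.3 repeats it: "Efficacy analyses will be carried out on the mITT set". Membership of the mITT set needs one dose and one evaluable post-dosing efficacy endpoint, by randomised arm. Violations play no part. SAP 4.2 and SAP 6 restate the rule.

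**Deviations in the SAP.** SAP 4.2 uses major deviations to define a separate PP set. The sponsor identifies them before database lock, and the PP analysis is optional. The SAP does not mention Protocol 9.5.9.

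**Timing and blinding.** Protocol 10.6 makes this a precondition of lock: "Decisions have been made and agreed as to the identities of all protocol violators". Protocol 9.5.7 says "Interim analyses will be performed at Days 19, 35, and 64 per 9.5.3 and 9.5.3.1 above", and 9.5.3 contains the primary comparison, "The group mean LMS difference between each Active Treatment Arm and the Vehicle Arm for the WOMAC pain score at Day 35". Protocol 9.2 and SAP 3.2.2 name subjects, site personnel and CRO personnel (other than the Medical Monitor) as blinded. They do not name the sponsor. SAP 8 leaves interim analyses outside its scope.

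**The concern.** A subject who meets the mITT definition but has a protocol violation is in the primary Day 35 analysis under one set of sections, and may be taken out under another. A statistician working from both documents cannot tell which applies.

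The 5% test level assumes that the choice of analysed data does not depend on the results. Agreeing who the violators are before lock is useful, but it is a different decision from choosing whose data, or which values, leave the efficacy analysis. Being before lock also does not make a decision blind when efficacy comparisons are planned at Days 19, 35 and 64. Reporting the reasons afterwards discloses an exclusion but cannot show that it was made independently of outcome.

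**Working it through.** **1. Texts side by side.** Take a dosed subject with a Day 35 WOMAC pain score and a protocol violation.

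| Source | Is the score in the primary analysis? |
|---|---|
| Protocol 9.3 and 9.5.3 | Yes: in mITT, no exception for violations |
| SAP 4.2 and 6 | Yes: in mITT; a major deviation removes the subject from PP only |
| Protocol 9.5.9 | At the sponsor's decision |
| Protocol 9.5.8 and SAP 4.4 | Yes, but with a qualifier limiting inclusion to where it is appropriate |

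The first two rows agree. The third is not tied to them by any cross-reference.

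**2. The plan's own figure.** SAP 9 gives 80% power for a difference of 63, SD 100 and 40 per arm. The check is 63 / (100 × √(2/40)) = 63 / 22.36 = 2.817, then 2.817 − 1.960 = 0.857, and Φ(0.857) = 80.4%. The noncentral t gives 79.5%. The figure reproduces.

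**3. Power cost of any exclusion, blind or not.** The same formula with 38, 36, 34 and 32 per arm (2, 4, 6 and 8 removed) gives 78.4%, 76.2%, 73.8% and 71.2%.

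**4. False-positive cost if the choice follows the results.** Inputs from the plan are 40 per arm and a two-sided 5% test, so 2.5% in active's favour. Assumptions are no true effect, m violators in each arm whose violations are unrelated to outcome, and a sponsor who knows the group results and keeps or drops all violators, whichever favours active. The documents give no violator count, so m runs from 2 to 8.

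The statistics with and without the violators have correlation ρ = √((40 − m)/40). A false result favouring active occurs if either one passes the limit:

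P = 2.5% + 2.5% − P(both pass)

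| m per arm | ρ | P(both pass) | P favouring active | Simulation, 400,000 trials | Repeat, 200,000 trials |
|---|---|---|---|---|---|
| 2 | 0.975 | 1.98% | 3.02% | 2.97% | 3.0% |
| 4 | 0.949 | 1.76% | 3.24% | 3.20% | 3.3% |
| 6 | 0.922 | 1.60% | 3.40% | 3.38% | 3.4% |
| 8 | 0.894 | 1.46% | 3.54% | 3.53% | 3.6% |

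The simulations use pooled t-tests. With no exclusion the larger run gives 2.46%. With all violators removed regardless of outcome it gives 2.46% (m = 4) and 2.48% (m = 6).

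Under the SAP 6.1 model (treatment, baseline and their interaction, with an assumed baseline-outcome correlation of 0.4 and 180,000 trials) the figures are 2.56% with no exclusion, 3.34% for m = 4 and 3.48% for m = 6.

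**5. Two-sided rate.** A false result favouring vehicle survives only if both statistics pass in that direction, with probability P(both pass). The total is (5% − P(both pass)) + P(both pass) = 5%. The simulations give 4.9% to 5.0%. Selection moves false positives towards active without adding to their number.

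**The case against.** The strongest reply is that the SAP already settles the matter. It governs the final analyses, keeps efficacy on mITT and uses deviations only for PP. SAP 4.3 adds that all data are analysed by recorded visit, although that sentence concerns visit windows. Most of this stands: the SAP's direction is clear. But it neither cites nor cancels 9.5.9, it refers readers to the protocol for full details, and SAP 4.4 keeps the appropriateness qualifier.

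A second reply is that 9.3 is a general rule and 9.5.9 a specific exception, so the two can be read together. That is arguable, which is why the mismatch is called unreconciled and not a flat contradiction.

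A third is timing. Violators are agreed before lock (Protocol 10.6), and SAP 4.1 releases the database to the CRO's biostatisticians for final analysis only after lock. This stands too. It would be wrong to say there is no timing control. Only knowledge of interim results could make the choice outcome-driven.

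A reader might infer that the sponsor is unblinded and will see those results. The documents do not say so. The blinding text omits the sponsor, no text says who receives interim results, and 9.5.7 ends on a comma and may be cut off. A reader might go further and suppose that the sponsor could pick out individual poor responders by arm. That needs subject-level treatment codes, which no text gives the sponsor, so no figure is offered for it.

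Finally, SAP 4.5 calls the study exploratory and makes no multiplicity adjustment. That limits the weight of any single p value, but it does not leave open which data are analysed.

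**Conclusion.** The point holds as a minor harmonisation fix. Protocol 9.5.9 contains a sponsor discretion over efficacy data, with no blinding condition, that the mITT rule does not provide for and the SAP does not withdraw.

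The illustrated effect is a rise from 2.5% to about 3.0% to 3.6% in the chance of a false result favouring active, for one active-versus-vehicle comparison. It rests on assumed violator counts (2 to 8 per arm) and on the sponsor knowing group results, which is not stated. The plan's two-sided error rate stays at about 5%, so the documents do not support a claim that 9.5.9 inflates it. If exclusions are unrelated to outcome, the cost is some power and no bias in the test.

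**What to change.** Delete the discretionary efficacy exclusion from Protocol 9.5.9, and put this text in both 9.5.9 and SAP 4.2:

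*No subject or value is excluded from the mITT efficacy analyses because of a protocol violation; the visit-selection and WOMAC scoring rules in SAP 4.3 and 4.6 still apply. Protocol deviations affect only the PP set, whose major deviations are identified before database lock and without knowledge of treatment assignment or interim group results.*

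The reference to SAP 4.3 and 4.6 is needed because those sections already set some recorded data aside: the value closest to the study visit is used when a visit has several, and a subscale is set to missing when too many components are absent.

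Also remove the condition in SAP 4.2 that makes the PP analysis optional, so that PP is always run for the primary endpoint as the sensitivity check.

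Cost: a short wording change in each document and one further analysis, with no extra subjects or procedures. The downside is that values affected by violations stay in the primary analysis, as the mITT rule already implies.
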